ANNEX 1: SAMPLE SIZE CALCULATIONS, TECHNICAL SPECIFICATIONS

Sample size calculation

The goal of the sample size calculations is to calculate the minimally required sample size that ensures desirable properties of the VE estimates. Examples of desirable properties are the expected length of the 95% CI, the expected lower half-width of the 95% CI or power to detect statistical significance of a pre-specified effect size. Two approaches to sample size calculations have been developed; analytical and simulation-based. While analytical methods do have the advantage of computational speed, simulation-based methods are sometimes developed to closer mimic the actual study design than proposed analytical approaches at the cost of requiring additional parameter assumptions.

Analytical approach: power and minimal detectable VE

The power is the likelihood of statistical significance when there is a true effect while the minimal detectable VE is the smallest VE that can be detected as significantly greater than zero in a given study using hypothesis testing. The power and minimal detectable VE can be derived from the 2x2 table of interest cross-tabulating the expected number of cases and controls with the expected number of subjects within the relevant exposure group and within the appropriate comparator group.

Particularly, to derived the power for case-control studies, first calculate

$$M = \left| \frac{(\lambda - 1)(P - 1)}{1 + (\lambda - 1)P} \right|,$$

and

$$p_c^* = \frac{P}{r+1} \left(\frac{r\lambda}{1+(\lambda-1)P} + 1 \right),$$

where λ is the relative risk, P is the exposure prevalence and r is the case-control ratio. Then, the power can be derived from

$$z_{\beta} = \frac{\frac{MP\sqrt{nr}}{\sqrt{r+1}} - z_{\alpha}\sqrt{(r+1)} p_{c}^{*}(1-p_{c}^{*})}{\sqrt{\frac{\lambda P(1-P)}{[1+(\lambda-1)P]^{2}}} + r P (1-P)},$$

where z_{α} and z_{β} are critical values for the standard normal distribution²⁰.

The minimal detectable VE for a case-control study is estimated as

$$VE_{MD} = 1 - RR_{MD(RR<1)},\tag{1}$$

²⁰ WOODWARD, M. (2013). *Epidemiology: Study Design and Data Analysis, 3rd Ed.*, Chapman and Hall/CRC.

where $RR_{MD(RR<1)}$ is the minimal detectable approximate relative risk (RR) in a case-control study, if RR < 1, or

$$RR_{MD(RR<1)} \cong 1 + \frac{-b - \sqrt{b^2 - 4a(r+1)}}{2a},$$
 (2)

where

$$a = r\gamma^2 - \frac{Nr\gamma(1-\gamma)}{\left(\frac{z_{\alpha}+z_{\beta}}{2}\right)^2(r+1)} \quad ; b = 1 + 2r\gamma,$$

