for 'cases to controls' ratio r, coverage γ , total number of subjects N, and where z_{α} and z_{β} are the standard normal z-scores for the type I and type II error rates²⁰.

For case-control studies with multiple exposure categories (k > 2), 3 generic exposure categories exist: (1) the exposure group of interest, (2) the appropriate comparator group and (3) other exposure groups not relevant for the comparison, resulting in a $3x^2$ cross table. Starting from the assumptions on the case-control ratio and on the proportions of subjects belonging to each of the three exposure categories (derived from assumptions on brand-specific vaccination coverage, overall vaccination coverage and vaccination history), the relative cell frequencies of the $2x^2$ table of interest can be derived, based on which all parameters required for sample size calculations are derived.

Simulation-based approach

Data generation workflow

Notation

Before describing the data generation workflow, the following parameters which act as input for the model have to be defined:

- 1. $VE_{x,overall}$: the overall VE of exposure x, the corresponding odds ratio is $OR_{x,overall} = 1 - \frac{VE_{x,overall}}{100}$.
- 2. c = P(unexposed | control): proportion of unexposed subjects among the controls
- 3. $P_x = P(exposure \ x | exposed, control)$: brand share of exposure x among the exposed
- 4. *r*: ratio of cases to control (that is, number of cases per one control)

General set-up

In each simulation run, a dataset is constructed by combining data generated for a number of individual Study Contributors. We will denote the total number of Study Contributors as k and the total sample size as N. Additionally, it is assumed that each Study Contributor contributes the same number of subjects, i.e. $\frac{N}{k}$. In order to allow for variability in the underlying vaccine effects across Study Contributors, the VE can be different from Study Contributor to Study Contributor. In the next section, it is described how data for one Study Contributor is generated given the Study Contributor-specific VEs for all exposures. The subsequent section describes how the VE are varied across the Study Contributors to introduce between-Study Contributor variability.

Simulating data at the Study Contributor level

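### Annex 1, equation (2), as printed returns RR above 1 and a negative minimal detectable VE; both the root and the z-term need correcting

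*Protocol*

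**What the plan says.** In the protocol's Annex 1 (Analytical approach: power and minimal detectable VE), the text states that the "minimal detectable VE is the smallest VE that can be detected as significantly greater than zero". Equation (1) sets "VE_{MD} = 1 - RR_{MD(RR<1)", where the relative risk on the right "is the minimal detectable approximate relative risk (RR) in a case-control study, if RR < 1". Equation (2) supplies that relative risk as "RR_{MD(RR<1)} \cong 1 + \frac{-b - \sqrt{b^2 - 4a(r+1)}}{2a}", with coefficients "a = r\gamma^2 - \frac{Nr\gamma(1-\gamma)}{\left(\frac{z_{\alpha}+z_{\beta}}{2}\right)^2(r+1)} \quad ; b = 1 + 2r\gamma".

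The inputs are the cases-to-controls "ratio r, coverage γ , total number of subjects N", and the z-terms are described as "standard normal z-scores for the type I and type II error rates". The Annex sets no condition on the sign of a and offers no second root. It gives no alpha, power, coverage, ratio or sample size for this formula. Section 11.10 refers to Annex 1 for the technical basis of sizing and leaves the calculations to each Study Requestor-specific protocol.

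**The concern.** The coefficient a contains a negative term that grows with N. Once a is negative, the two roots in RR - 1 have opposite signs, so only one of them can be the protective solution. The printed choice, minus the square root over 2a, is the other one. Equation (1) then turns a relative risk above 1 into a negative VE, which cannot be the smallest VE detectable as greater than zero.

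A second problem would surface as soon as the sign is repaired. The printed a divides by the square of half of (z_alpha + z_beta), which makes that divisor four times too small. The sign-corrected result then looks plausible but is far too optimistic about what the study could detect. Requestor-specific protocols that apply the Annex formula would carry this into their statements of what a given N can show.

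**Working it through.** **Inputs.** Equations (1) and (2), a, b and the power formula are from Annex 1. Assumed, because the protocol gives none: two-sided alpha 5% (z = 1.960) and power 80% (z = 0.842). N, r and coverage are illustrative. The protocol states no minimal detectable VE, so there is no figure to reproduce.

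**Where the quadratic comes from.** In the power formula put n = N, λ = 1 + d, P = γ, and use the alternative-hypothesis variance for both z-terms. With K the squared z-term:

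(MP)²·N·r/(r+1) = K·[λP(1-P)/(1+dP)² + rP(1-P)]

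Multiply by (1+dP)² and divide by K·P(1-P):

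d²·N·r·P(1-P)/(K(r+1)) = (1 + d) + r(1 + dP)²

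Collecting terms gives a·d² + b·d + (r+1) = 0, with a = rP² - N·r·P(1-P)/(K(r+1)) and b = 1 + 2rP. These are the Annex coefficients, except that the derivation gives K = (z_alpha + z_beta)² = 7.849, whereas the printed divisor is ((z_alpha + z_beta)/2)² = 1.962.

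**Sign of a.** a < 0 when N > γ(r+1)K/(1-γ). For r = 0.1 to 0.25 and K = 7.849 this threshold is about 1 subject at 10% coverage and 9 to 10 subjects at 50%; with the printed divisor it is a quarter of that. With a < 0 and b > 0, sqrt(b² - 4a(r+1)) exceeds b. The minus root is therefore negative over negative, so d > 0 and RR > 1. The plus root gives RR < 1.

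Over a grid of 5,544 settings (N 100 to 20,000, r 0.02 to 2, coverage 1% to 80%, alpha 5% or 10%, power 80% or 90%, both readings of the divisor), the minus root exceeded 1 in 5,542. The other two had a > 0 and gave an impossible negative RR.

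**One case in full: N = 1000, r = 0.25, γ = 0.20.**
- b = 1 + 2 × 0.25 × 0.20 = 1.10.
- Printed divisor: a = 0.01 - 40/(1.962 × 1.25) = -16.30, and the square root is sqrt(1.21 + 81.49) = 9.094. Minus root: d = -10.194/-32.60 = +0.313, so RR 1.313 and VE -31.3%. Plus root: d = 7.994/-32.60 = -0.245, so VE 24.5%.
- K = 7.849: a = 0.01 - 40/(7.849 × 1.25) = -4.067, and the square root is sqrt(1.21 + 20.34) = 4.642. Minus root: VE -70.6%. Plus root: d = 3.542/-8.134 = -0.435, so VE 43.5%.

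**Putting 24.5% back into the Annex power formula** (each radical read as covering its full expression): λ = 0.755 gives M = 0.206 and p_c* = 0.192. The numerator is 0.583 - 0.863 = -0.279 and the denominator 0.417, so z_beta = -0.67 and power is about 25%.

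**All cases.** The last column is the VE at which the Annex power formula itself gives 80%.

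| N, r, coverage | As printed | Plus root, printed divisor (power) | Plus root, K = (z_alpha + z_beta)² (power) | Power formula at 80% |
|---|---|---|---|---|
| 1000, 0.25, 20% | -31.3% | 24.5% (25%) | 43.5% (72%) | 46.8% |
| 2000, 0.1, 10% | -42.9% | 30.7% (21%) | 52.2% (61%) | 61.0% |
| 5000, 0.1, 10% | -25.5% | 20.7% (24%) | 37.2% (69%) | 41.2% |
| 1000, 1, 30% | -20.9% | 17.9% (29%) | 33.2% (80%) | 33.3% |

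With both corrections the equation agrees with the power formula at r = 1. It is optimistic when cases are few relative to controls, because equation (2) uses one variance where the power formula uses a pooled variance for the null term.

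**The case against.** The strongest reply concerns reach. The Annex names CI length, lower half-width and power as its example sizing properties, and minimal detectable VE is not among them. The protocol reports no number from equation (2), and power and simulation methods are also described. A negative minimal detectable VE is self-revealing, and nothing shows that any calculation used the printed root. All of this stands, and it limits the severity.

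The second reply is that the text was extracted from PDF and Annex 1 shows other damage of that kind. The minus sign might be misread, and the halving of the whole z-sum might be a garbled z for alpha/2. This also stands as a reason to check the original first. The sign argument holds under either reading of the divisor.

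Two stronger readings are tempting. A reader might infer that one sign change cures the formula. It does not: with the printed divisor, the sign-corrected VE has 21% to 29% power instead of 80% in the cases shown. A reader might also infer that existing brand-specific sample sizes are wrong, or that someone has reported the harmful-direction figure with its sign dropped. The document contains no such figure and supports neither inference.

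**Conclusion.** As it reads, equation (2) is wrong. At any usable N it returns RR above 1 and a negative minimal detectable VE, against its own label and the Annex's definition. The direction follows from the signs of a and b alone and does not depend on the assumed alpha, power, ratio or coverage. The sizes do: -21% to -43% as printed in the four cases above, against 33% to 61% from the Annex power formula at assumed two-sided 5% alpha and 80% power.

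The z-term in a is a second error in the same equation. Even with both repaired, the equation only approximates the power formula when r is far from 1 (52% against 61% at N = 2000, r = 0.1, coverage 10%).

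This is a should-fix, conditional on the sign and the z-term reading the same way in the original PDF. It touches no patient, estimand or analysis in this document, but it sits in the sizing template for later protocols.

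**What to change.** Check the sign before the square root and the z-term in a against the original PDF. If they read as here:

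1. In equation (2), use -b + sqrt(b² - 4a(r+1)) over 2a for RR < 1.
2. In a, replace ((z_alpha + z_beta)/2)² by (z_alpha + z_beta)², and state that z_alpha is the two-sided critical value if the test is two-sided.
3. State that equation (2) approximates the Annex power formula and is optimistic when cases are few relative to controls. Alternatively, drop it and solve the power formula numerically for RR < 1.
4. Recompute any minimal detectable VE already derived from the printed form. When putting a result back into the power formula, expect close agreement only near r = 1; a gap elsewhere does not mean that the sign correction is wrong.

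The cost is an edit to one equation and one sentence in Annex 1, plus a re-run of any sizing table that used it. No data collection or recruitment changes.

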For each simulated dataset, an estimate of the (r)VE and the corresponding 95% CI is obtained using one of the following procedures:

²¹ THOMPSON, M. G., STENEHJEM, E., GRANNIS, S., et al. (2021). Effectiveness of Covid-19 Vaccines in Ambulatory and Inpatient Care Settings. N Engl J Med, 385(15):1355-71. DOI: https://doi.org/10.1056/NEJMoa2110362.

Two-stage pooling / random-effects meta-analysis (RE-MA)

- The simulated dataset is restricted to represent the data of interest.
- The Study Contributor-specific expected OR on the log-scale of the (relative) treatment effect is calculated using a logistic regression model with the disease status as the outcome and the exposure status as a covariate.
- The Study Contributor-specific log OR estimates are combined using a random-effects metaanalysis (RE-MA) model. More particularly, the log OR estimates are combined using the Hartung-Knapp-Sidik-Jonkman estimator to obtain an estimate of the median overall log OR and the corresponding two-sided 95% CI.
- The pooled log OR and the corresponding CI are then back-transformed to obtain an estimate and 95% CI of the median overall VE.
- The overall VE estimate and the length of the CI are stored for each simulation.

Generalised estimation equations (GEE)

- The simulated dataset is restricted to represent the data of interest.
- The expected OR on the log-scale of the treatment effect is estimated using a logistic regression model with the disease status as the outcome and the exposure as a covariate. The estimates are obtained using the GEE method in which the Study Contributors are considered as clusters and the variances are calculated using a robust sandwich estimator.
- The estimated log OR and the corresponding CI are then back-transformed to obtain an estimate of the mean overall (r)VE and its 95% CI.
- The overall (r)VE estimate and the length of the CI are stored for each simulation.

Generalised linear model/generalised additive model (GLM/GAM)

- The simulated dataset is restricted to represent the data of interest.
- The expected OR on the log-scale of the treatment effect is estimated using a logistic regression model with the disease status as the outcome and the exposure as a covariate.
- The estimates are obtained using the GLM/GAM method in which the Study Contributors are considered as fixed effects.
- The estimated log OR and the corresponding CI are then back-transformed to obtain an estimate of the mean overall (r)VE and its 95% CI.
- The overall (r)VE estimate and the length of the CI are stored for each simulation.

Number of simulations performed

For each combination of parameter settings, a total of 500 simulations are recommended. On empirical basis, this number of simulation runs leads to stable Monte Carlo CIs while limiting the computational burden.

Summary measures of the simulation study

For each combination of the study characteristics, the measure of interest is obtained from the 500 simulations, e.g.

- The expected range of the 95% CI is defined as the mean range of the CI obtained from the 500 simulations.
- The expected lower half width of the 95% CI is defined as the mean lower half width of the CI obtained from the 500 simulations.
- The expected power to detect a VE significantly different from 0 is defined as the proportion of the CIs that do not include 0.

For each measure, 95% Monte Carlo CIs were constructed based on the respective Monte Carlo standard errors observed in the simulations.
